8.1 Definition of Analysis Sets

Screening Analysis Set (SCR)

The Screening analysis set (SCR) includes all participants who signed the informed consent.

Enrolled Analysis Set (ENR)

Patients in the SCR who met eligibility criteria.

Full Analysis Set (FAS)

Patients in the Enrolled Analysis Set (ENR) who were treated with at least one course of treatment with cladribine tablets.

8.2 Subgroup Definition and Parameterization

Subgroup analyses will be performed on primary and secondary outcomes. All subgroup analyses will be exploratory, no adjustment for multiplicity will be performed.

The following subgroups will be defined:

Most recent prior disease-modifying therapy:

- Naïve to disease-modifying therapies
- Prior platform therapy
- Prior high-efficacy cell-depleting treatment
- Prior high-efficacy non-depleting treatment

Prior and subsequent disease-modifying therapies will be medically reviewed on an ongoing basis and classified by the medical advisor. This process will be described in a separate document. DMTs classes will be linked with electronic case report form (eCRF) data for data analysis.

9 General Specifications for Data Analyses

Index date

Cladribine initiation date will be used as an index date to determine baseline and on-treatment periods.

Initial date

According to the protocol, data will be collected counting from 1 year prior to cladribine initiation date. The initial date will be calculated as follows:

- Initial date: Index date/cladribine initiation date - 1 (year).

All assessments occurred from initial date onwards will be considered for the analysis.

Pre-treatment period is defined as follows:

- Pre-treatment: from initial date until cladribine initiation date - 1 (day).

Listings

In the individual participant data listing all individual data will be listed as measured. Repeated measurements will be included in the listings. All listings will be sorted by subject ID, study period, and date of assessment as appropriate.

Tables and Descriptive Statistics

All data will be summarised by the most recent prior DMT group and overall. Repeated measurements (in the same time window) included in the listings will not be used for statistical analyses or summaries unless the repeated measurement was performed due to unreliable values/technical reasons.

Unless otherwise specified, continuous variables will be summarised using descriptive statistics, i.e. the number of participants with non-missing values (n), the number of participants with missing values, (nmiss), mean, standard deviation (SD), median, 25th percentile (Q1) and 75th percentile (Q3), minimum, and maximum. If there are no missing values, the number of participants with missing values should be indicated by a 0.

Qualitative variables will be summarised by frequency counts and percentages. Unless otherwise stated the calculation of proportions will be based on the number of participants of the analysis set of interest. Therefore, counts of missing observations will be included in the denominator and presented as a separate category.

All analyses will be performed using SAS® Software version 9.4 or higher.

9.1 Definition of Baseline and Change from Baseline

In general, the last non-missing measurement prior to the index date (i.e. cladribine initiation date) will be used as the baseline measurement for analyses that require change from baseline calculation (e.g. EDSS analysis).

If an assessment is performed on the same day as cladribine initiation it will be assumed that it was performed prior to treatment start and will be considered as baseline. Last non-missing measurements occurred more than 60 days before cladribine initiation will not be considered 'baseline'.

Changes from baseline are defined as:

$$\text{Change} = \text{visit/year value} - \text{baseline value}$$

9.2 Study Day

Day 1 is the day of cladribine initiation date (i.e. index date), the day before is Day -1 (no Day 0 is defined). Study day is defined relative to Day 1.

9.3 Definition of Duration and ‘Time Since’ Variables

Durations in days will be calculated by the difference of start and stop date + 1 (e.g. duration of diagnosis at cladribine initiation (days) = date of MS diagnosis – date of cladribine initiation + 1) if not otherwise specified.

9.4 Conversion Factors

The following conversion factors will be used to convert days into months or years:

1 week = 7 days, 1 month = 30.4375 days, 1 year = 365.25 days.

9.5 Date of Last Contact

The date of last contact will be derived for participants not known to have died at the analysis cut-off using the latest complete date prior to or at the data cut-off date among the following:

- AE start and end dates
- Cladribine start and end dates
- DMT start and end dates
- Concomitant medications/procedures start and end dates
- Onset of relapse and stabilisation/resolution dates
- EDSS assessment dates
- Lab collection dates
- MRI scan dates

Assessment dates after the cut-off date will not be applied to derive the last contact date. Imputed dates will contribute to the last contact date derivation if the month and year are available and only the missing day is imputed.

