#### **9.2.1.1                            Inclusion Criteria**

For inclusion in the study, all of the following inclusion criteria must be fulfilled:

1. At least 18 years of age at cladribine tablet treatment initiation
2. Physician diagnosis of HDA-RRMS as defined by clinical or radiological features
3. Treatment initiation with cladribine tablet monotherapy on or after 22 August 2017 and at least 3 years before enrolment
4. Completion of Year 1 treatment of cladribine tablets (Week 1 and Week 2 treatment, per recommended dose in Year 1: 1.75 mg/kg body weight, cumulatively)
5. Provide written informed consent to participate in the study

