## 9.2.3 Observation Period

The total observation period per patient will vary, depending on the pre-enrolment time on cladribine tablet treatment (i.e., the period between the date of cladribine tablet initiation and study enrolment date). The observation period per patient, counting from 1 year prior to cladribine tablet initiation until the date of the second chart review, will be at minimum 5 years and at maximum 7 years.

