#### Primary Outcome Analysis

The annualised relapse rate for a patient is defined as the number of clinician's confirmed relapses that occurred in the year prior to the date of cladribine tablet initiation, and in Years 1, 2, 3, 4 and 5 after treatment initiation with cladribine tablets (upon availability, depending on the available observation time):

- Year prior to date of cladribine tablet initiation: Month -12 to the day before the date of cladribine tablet initiation (Start Month 1)
- Year 1: Start Month 1 to End of Month 12
- Year 2: Start Month 13 to End of Month 24
- Year 3: Start Month 25 to End of Month 36
- Year 4: Start Month 37 to End of Month 48
- Year 5: Start Month 49 to End of Month 60

Relapses will be counted for the defined time period if the date of onset of the relapse is within the defined time period. In the analyses defined in the IAP, an "induction period" after treatment initiation may be considered for the annualised relapse rate in Year 1.

The annualised relapse rate for a patient will be calculated by dividing the number of clinician confirmed relapses during the period by the person-years of the patient (i.e., the period [in days] that a patient was observed in the study divided by 365.25).

The estimated annualised relapse rate in each of the defined years above will be summarised using descriptive statistics for continuous variables.

The annualised relapse rate will be described overall and among the subgroups by most recent prior DMT, as defined in [Table 2](#).

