To evaluate the subsequent disease modifying therapies (DMTs) received after cladribine tablets discontinuation up to 5 years after cladribine tablets initiation.	Effectiveness: 
 - Number of subsequent DMTs. - Number and % of patients who received subsequent DMTs. - Time to first subsequent DMT from last dose of cladribine. - Time to second subsequent DMT from last dose of cladribine. 	14.2.3
To analyse the proportion of patients with disability progression confirmed over 6 months, 2 years after treatment initiation.	Effectiveness: 
 - Change from baseline to year 2 in EDSS - Number and % of patients with disability progression confirmed over 6 months. 	14.2.4
To analyse the incidence of selected, identified, and potentially clinically important adverse events (AEs).	Safety: 
 - Number and % of patients with AEs - Number and % of patients with AEs by preferred term (PT) and system organ class (SoC). 	15.1
Others		
To evaluate MS-related lesions as assessed by MRI in patients with HDA-RRMS after cladribine tablet initiation.	Effectiveness: 
 - Number and % of patients with: 
 o T1 gadolinium enhancing lesions, o T2 new lesions, o T2 enlarging lesions. 	16.1

6 Overview of Planned Analyses

The final analysis will be performed once the study is completed with the purpose of evaluating all outcomes and the database is locked. The final analysis will include data collected during the first and the second chart abstractions. The database will be locked once the second chart abstraction is completed on all patients unless they withdrew consent, discontinued the study, or were lost to follow-up.

7 Changes to the Planned Analyses in the Clinical Study Protocol

There are no changes to the planned analyses in the clinical study protocol.

8 Analysis Sets and Subgroups

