- Number of tablets taken per week of ‘Year 1’, ‘Year 2’ and each subsequent course of cladribine
- Total number of tablets taken on ‘Year 1’, ‘Year 2’ and each subsequent course of cladribine
- Cumulative number of tablets taken (cumulative over Year 1 and Year 2, and cumulative over all courses of cladribine treatment)
- Number % of patients with no dose and dose delayed (with the corresponding reasons)
- Number % of patients with a complete course of cladribine at ‘Year 1’, ‘Year 2’, any additional courses of cladribine treatment and overall

14 Effectiveness

The following analyses will be performed based on the FAS by the most recent prior DMT and overall.

14.1 *Primary Outcome: ARR*

14.1.1 *Primary Objective: Derivation and analysis of the primary outcome: ARR*

The annualised relapse rate (ARR) will be derived from the 'Clinical Confirmed Relapses' CRF page.

The relapses observed will be assigned for the calculation for the ARR as indicated on [Table 1](#) in Section 9.6.

The ARR for a patient will be calculated by dividing the number of clinicians confirmed relapses observed within each period (Year) by the person-years of the patient in the period.

The person-years for a patient will be assigned as follows:

- $(365.25-84)/365.25$ years for time-point 'Year 1' for the full effectiveness period (main analysis)
- $(365.25-56)/365.25$ years for time-point 'Year 1' for the amplified effectiveness period (sensitivity analysis #1)
- 1 year for time-point 'Year 1' for the full treatment effectiveness period (sensitivity analysis #2)

And 1 year for each other interval (-1, 2, 3, 4, 5) unless the date of last contact occurs within that interval. In this case that interval person-years will be calculated until the date of last contact. The patient will not contribute to the ARR calculation for the following intervals (if any).

The 95% confidence interval (CI) will be calculated using the exact Poisson method.

14.2 *Secondary Outcomes*

14.2.1 *Secondary Objective: Derivation and analysis of the secondary outcome: RFR*

The relapse-free rate (RFR) is defined as the time from the on-treatment period start date (see [Table 3](#)) until the date of the first relapse or death as assessed by the investigator:

- RFR (years): $(\text{First relapse date or death or date of censoring} - \text{on-treatment start date} + 1) / 365.25$.

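### Follow-up for ARR, RFR and T1DMT ends at the last dated record instead of the second chart review, which biases ARR upward in Years 4 and 5, most in Year 5

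*SAP*

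**What the plan says.** SAP 9.5: "The date of last contact will be derived for participants not known to have died at the analysis cut-off using the latest complete date" among eight kinds of record: AE, cladribine, DMT, concomitant medication or procedure, relapse (onset and resolution), EDSS, laboratory and MRI dates. Consent and the two chart reviews are not on the list.

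SAP 14.1.1 gives each interval other than Year 1 a full person-year "unless the date of last contact occurs within that interval"; in that case the interval is cut at last contact and the patient is dropped from all later intervals. On precision it says: "The 95% confidence interval (CI) will be calculated using the exact Poisson method". SAP 14.2.1 and 14.2.3 censor RFR and T1DMT at the same date.

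Protocol 9.7.3 (Primary Outcome Analysis) divides by a different quantity: "the period [in days] that a patient was observed in the study divided by 365.25". Protocol 9.2.3 describes observation as "counting from 1 year prior to cladribine tablet initiation until the date of the second chart review", and 9.1.1 has the second abstraction collect data up to its own date. Patients must have started cladribine "on or after 22 August 2017 and at least 3 years before enrolment". SAP section 7 nevertheless states: "There are no changes to the planned analyses in the clinical study protocol".

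**The concern.** The denominator of the primary outcome depends on the outcome. A patient who relapses late gains person-time up to the relapse and its resolution. A patient who stays well is followed only to the last dated entry of some other kind, even though the site later examined the chart and found no relapse.

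Take a relapse-free patient with no dated entry after Month 30. The rule keeps half of Year 3 and nothing of Years 4 and 5. The second review comes at least 4 years (48 months) after initiation, so at least 18 months of reviewed, relapse-free time is discarded. At least 6 of those months precede the patient's own consent, which cannot come before Month 36.

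The error grows with time since initiation, because that is where the last record and the review date come apart. A rise in ARR in Years 4 and 5 could be read as waning effect when it comes from the denominator. If record frequency differs by site or prior-DMT subgroup, the subgroup pattern is distorted too.

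**Working it through.** **The plan's own figure.** Protocol 9.5 gives a distance of 0.072 from the estimate to the 95% limit for an ARR of 0.14 and 90 patients. It reproduces as a binomial half-width: 1.96 × √(0.14 × 0.86 / 90) = 0.0717. It does not depend on the last-contact rule.

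**Direction.** Protocol 9.3 has each relapse recorded with at least month and year, and SAP 9.5 lets dates with only the day imputed count. A relapse so recorded cannot fall after last contact. The number of relapses is then the same under either rule and person-time can only be shorter, so total relapses over total person-years is never lower than with follow-up to the second review.

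**Two-patient example, Year 5 (days 1462 to 1826), both reviewed on day 1826.**
- No relapse, last laboratory date day 1500: (1500 − 1462 + 1) / 365.25 = 0.107 person-years.
- Relapse on day 1700, resolved day 1730: (1730 − 1462 + 1) / 365.25 = 0.736 person-years.
- SAP rule: 1 / 0.843 = 1.19. Follow-up to the review: 1 / 2.0 = 0.50.

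**Simulation inputs.**
- From the protocol: ARR 0.14 (9.5); total observation of 5 to 7 years including one year before initiation (9.2.3), hence a second review 4 to 6 years after initiation; consent one year before that review.
- Assumed: review times uniform over 4 to 6 years; constant relapse rate; a cladribine record at 1.1 years for all; relapse resolution after 1 to 3 months; record frequencies as shown.
- 400,000 patients per scenario; yearly ARR is total relapses over total person-years; RFR is Kaplan-Meier from day 84.

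| Non-relapse records | ARR Y3 | ARR Y4 | ARR Y5 | Y5 person-time kept | 5-year relapse-free | Last contact before consent |
|---|---|---|---|---|---|---|
| Six-monthly | 0.14 | 0.14 | 0.17 | 84% | 0.50 | 0% |
| Yearly, regular | 0.14 | 0.15 | 0.20 | 69% | 0.47 | 2% |
| Random, mean 1 per year | 0.15 | 0.18 | 0.26 | 54% | 0.42 | 31% |
| Yearly, but 25% of patients with none after Year 2 | 0.17 | 0.19 | 0.25 | 55% | 0.41 | 23% |
| Follow-up to second review | 0.14 | 0.14 | 0.14 | 100% | 0.51 | – |

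The Year 5 column can be checked by hand as true rate over share of person-time kept: 0.14/0.84 = 0.17, 0.14/0.69 = 0.20, 0.14/0.54 = 0.26, 0.14/0.55 = 0.25. The true 5-year relapse-free probability is exp(−0.14 × (5 − 84/365.25)) = 0.513.

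**Wider range.** A further run (30,000 patients per scenario, SAP Table 1 windows, resolution after 60 days) gives these ratios of SAP-rule ARR to ARR with follow-up to the second review:

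| Records | Year 3 | Year 4 | Year 5 |
|---|---|---|---|
| 4 per year, even | 1.00 | 1.01 | 1.09 |
| 2 per year, even | 1.00 | 1.02 | 1.19 |
| 1 per year, even | 1.00 | 1.08 | 1.46 |
| 0.5 per year, even | 1.03 | 1.34 | 2.24 |
| 2 per year, random | 1.01 | 1.10 | 1.41 |
| 1 per year, random | 1.08 | 1.30 | 1.86 |

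Years 1 and 2 stay at 1.00 to 1.03. With one evenly spaced record per year, the Year 5 ratio is 1.49 at a true rate of 0.05 and 1.41 at 0.30, so the result hardly depends on the relapse rate.

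**Precision.** With 200 patients, expected Year 5 person-years are 150 to the second review, against 126, 103 and 81 under the SAP rule (six-monthly, yearly, random yearly). Coverage of the exact Poisson 95% interval for Year 5 is then 89%, 66% and 32%; with 90 patients it is 93%, 83% and 64%. Follow-up to the second review gives 96% to 97%.

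**What drives it.** Leaving out resolution dates barely moves Year 5 ARR (0.167, 0.207, 0.265 and 0.262 for the four patterns in the first table). The cause is the lack of an event-independent end date, so deleting relapse dates from the list would not cure it.

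**The case against.** **Records may be frequent.** Last contact pools eight sources, including lymphocyte counts, all AEs and concomitant medication, and protocol 9.1.2.2 describes EDSS as part of routine annual assessment. With quarterly records the excess is only about 1% in Year 4 and 9% in Year 5. This stands as a limit on the size: the sparse scenarios have no support in the documents, and with regular records Year 4 moves little. But nothing guarantees quarterly records. Data are taken as available, and protocol 9.3 names EDSS scores only to 2 years. An annual assessment alone is the yearly scenario, with a Year 5 ARR of 0.20.

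**The benchmark assumes complete charts.** Ending at the second review returns 0.14 because every relapse up to then is taken as captured. If care moved elsewhere undocumented, silence in the chart is not evidence of no relapse. This is the strongest point. If 10% or 20% of patients moved at a random time after Year 2 (assumption), ending at the review gives a Year 5 ARR of 0.13 or 0.12, while the present rule gives about 0.17 with six-monthly and 0.21 with yearly records. At 20% with six-monthly records the two errors are of similar size. That supports keeping both analyses; it does not support an event-dependent denominator as the main one.

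**The SAP may only be filling in detail.** Protocol 9.7.3 gives no explicit end date, and 9.7.2 leaves derivations to the analysis plan. That is fair as far as it goes. But follow-up that can end before consent is hard to reconcile with time observed in the study.

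**The planned estimator may be a mean of patient-level rates.** That does not help: its Year 5 bias is larger, at about 0.17 to 0.18, 0.22 to 0.23 and 0.30 to 0.31 for the six-monthly, yearly and random yearly patterns.

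**The study is descriptive, without a hypothesis test.** True, but yearly ARR to Year 5 is its primary result, and a biased estimate misleads with or without a test.

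**Conclusion.** The concern holds. As written, the rule gives a biased primary outcome, and relative to follow-up to the second review the direction is fixed by the definition: pooled ARR too high. Relapse-free probability is understated because relapse-free patients are censored early while every first relapse is counted. The same mechanism applies to T1DMT, since subsequent DMT dates are on the list; its size was not calculated.

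Across the record frequencies examined, from four per year to one every two years, the excess is about 9% to 124% in Year 5 and 1% to 34% in Year 4. It is negligible in Years 1 to 3 when records come at least yearly and regularly. These sizes rest on the assumed record frequency, the uniform review times and charts that capture relapses up to the review. The direction against the protocol's observation period does not rest on the assumed frequencies.

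**What to change.** - End ARR person-time and RFR/T1DMT censoring at a date that does not depend on events: the second chart review for completers, otherwise withdrawal, documented loss to follow-up or death, and never before the consent date.
- State the person-time end for deaths in SAP 14.1.1; SAP 9.5 covers only participants not known to have died.
- State that each yearly ARR is total relapses over total person-years, which is what the exact Poisson interval implies.
- Keep the present last-contact rule as a sensitivity analysis, as the other bound if transfers of care went undocumented. For that analysis, remove the circularity whereby SAP 9.10 imputes the end of an ongoing relapse to last contact while 9.5 derives last contact from relapse end dates.
- Record in SAP section 7 any departure from the protocol's definition of observed time.

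The cost is SAP wording and programming. No new data are needed, because SAP 10.1 already tabulates the timing of the second review. The price is the modest understatement of ARR described above if patients left the site's care without this being recorded.

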9.6 Time Window

For analyses conducted at yearly intervals (e.g. relapse rate at each year) the date of the event will be assigned an analysis time-point according to [Table 1](#):

Table 1. Time windows for relapses analysis

Time-point	Study day	
	From	To
Year -1	-365	-1
Year 1	84*	365
Year 2	366	731
Year 3	732	1096
Year 4	1097	1461
Year 5	1462	1826

*Relapses occurred within the induction period window of 12 weeks (84 days) will not be included in the main analysis. Sensitivity analyses will be repeated changing Year 1 interval to (56 to 365 days) and (1 to 365 days) respectively.

For EDSS analysis on disability progression the [Table 2](#) will be followed:

Table 2. Time window for EDSS analysis

Time-point	First assessment		
	Study day		
	From	Mid-point	To
Baseline	-60	-	1
Year 2 (treatment start date) OR Year 2	183	365	548

The closer assessment to the Year 2 treatment start date will be used. If the patient does not receive any treatment at Year 2, [Table 2](#) time-window will be used to derive the Year 2 EDSS assessment. The confirmatory EDSS score assessment (used to confirm disability progression) will be selected in the (+91; +272) days interval from the 'Year 2' assessment date. In case of multiple assessments within this window the closer to +182 days from the 'Year 2' assessment date will be picked.

In case of multiple assessments at the same distance of the mid-point the earliest one will be considered for the analysis. All measurements will be listed.

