### 9.1.2.2 Secondary

- Proportion of patients who remain relapse-free in each year and at 4 and 5 years after initiation of cladribine tablet treatment
- Time from cladribine tablet initiation to first relapse
- Proportion of patients who discontinued cladribine tablets and reasons for discontinuation
- Subsequent DMTs (none or by DMT type) received after cladribine tablets discontinuation/treatment completion up to 5 years after cladribine tablets initiation
- Disability assessed by the EDSS at treatment initiation and start of treatment Year 2

The EDSS is a neurological assessment to evaluate disability in patients with MS, performed by the physician. The annual EDSS at cladribine tablet treatment initiation and start of treatment Year 2 will be recorded, where available in the patients' notes. EDSS is routinely collected as part of standard care in the UK as part of the annual assessment required for continuation of treatment.

- Proportion of patients with disability progression confirmed over 6 months, assessed by the EDSS, at 2 years after cladribine tablet treatment initiation

An EDSS progression is defined as an increase in the EDSS scale as follows:

- If the EDSS score at cladribine tablet initiation is 0, the increase must be  $\geq 1.5$  units
- If the EDSS score at cladribine tablet initiation is  $\geq 0.5$  or  $\leq 4.5$ , the increase must be  $\geq 1.0$  units
- If the EDSS score at cladribine tablet initiation is  $\geq 5.0$ , the increase must be  $\geq 0.5$  units.

A confirmed disability progression is defined as EDSS progression (as defined above) confirmed after 6 months.

- Rates of selected, identified, and potentially clinically important AEs, including:

- grade 3 lymphopenia
- grade 4 lymphopenia
- herpes infections
- serious infections (infections for which a hospitalisation is initiated or extended)
- opportunistic infections (new onset or reactivation of latent infection)
- malignancies

These AEs will be reported from the date of cladribine tablet initiation and will be described overall and by most recent prior DMT subgroups (DMT naïve, prior platform treatment, prior high-efficacy cell-depleting treatment, and prior high-efficacy non-depleting treatment).

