- T1DMT (years): (Date of start of first subsequent DMT - last cladribine administration date + 1)/365.25.

Patients who did not start any subsequent DMT will be censored at the date of last contact.

The T1DMT will be summarised using the total number and % of patients with an event. The number and % of censored patients will be also presented.

The T1DMT and associated 95% CI will be summarised at yearly intervals using the KM method, the median TSDMT and corresponding 95% CI (whenever estimable) will be also included. KM curves will be provided.

Time to second subsequent DMT (T2DMT) will be derived as follows:

- T2DMT (years): (Date of start of second subsequent DMT - last cladribine administration date + 1)/365.25.

The T2DMT will be summarised in the same way of T1DMT only if at least 5% of patients have a second subsequent DMT recorded.

14.2.4 *Secondary Objective: Derivation and analysis of the secondary outcome: EDSS and disability progression*

The Annual EDSS results at cladribine initiation and at Year 2 and the corresponding change from baseline (i.e. cladribine initiation) will be summarised using descriptive statistics. Scores will be derived from the 'Annual EDSS scores' CRF page. All other assessment will be presented in a listing.

The number and % of patients with disability progression confirmed over 6 months at Year 2 after cladribine initiation will be also summarised.

EDSS progression is defined as an increase in the EDSS scale as follows:

- If the EDSS score at cladribine tablet initiation is 0, the increase must be ≥ 1.5 units
- If the EDSS score at cladribine tablet initiation is ≥ 0.5 or ≤ 4.5 , the increase must be ≥ 1.0 units
- If the EDSS score at cladribine tablet initiation is ≥ 5.0 , the increase must be ≥ 0.5 units.

EDSS assessments will be assigned to time windows as defined in Section 9.6.

15 Safety Analyses

Safety analyses will be performed based on the FAS by the most recent prior DMT and overall.

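### SAP 9.6 contradicts itself on whether the Table 2 window limits the Year 2 EDSS of patients treated in Year 2; read literally, its text can replace a missing score with the baseline or a roughly 2-year score

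*SAP*

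**What the plan says.** Two sentences below Table 2 in SAP 9.6 select the Year 2 EDSS. The first, for patients with a Year 2 course, reads "The closer assessment to the Year 2 treatment start date will be used". The second brings in the Table 2 window under a condition: "If the patient does not receive any treatment at Year 2". Taken together, they attach the Day 183 to 548 limits to untreated patients only.

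Other text points the other way:
- The table is introduced with "For EDSS analysis on disability progression the", followed by a statement that Table 2 governs. Treated patients are not exempted.
- The only follow-up row is labelled "Year 2 (treatment start date) OR Year 2" and carries one set of limits: 183, mid-point 365, 548.
- SAP 14.2.4 says "EDSS assessments will be assigned to time windows as defined in Section 9.6", again without an exemption.

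Three further provisions matter. SAP 9 (Initial date) sets the data scope: "All assessments occurred from initial date onwards will be considered for the analysis". The initial date is one year before initiation, so pre-treatment scores are in scope. SAP 9.10 says data are evaluated as observed, with no imputation unless otherwise specified. Protocol 9.1.2.2 makes the scores dependent on the notes: "The annual EDSS at cladribine tablet treatment initiation and start of treatment Year 2 will be recorded, where available".

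**The concern.** A programmer who follows the two sentences would search all of a treated patient's EDSS records for the one nearest the Year 2 start, with no limit on distance and no requirement that the score be post-baseline. Protocol 9.3 plans three scores: at the Year 1 start, at the Year 2 start and 2 years after initiation. If the middle one is absent, the search must return one of the other two.

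A baseline pick makes the change exactly 0 and rules out progression. In effect it carries the baseline forward, against SAP 9.10. A 2-year pick puts a later value under the Year 2 start label and moves the confirmation interval with it. In both cases a patient who should be counted as missing is not. The EDSS summary and confirmed progression are named secondary outcomes, reported overall and by prior-DMT subgroup.

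**Working it through.** **Plan's own figures.** With the SAP 9.4 factor of 30.4375 days per month, 6, 12 and 18 months are 182.6, 365.3 and 547.9 days. This reproduces Table 2's 183, 365 and 548.

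**Inputs.** Baseline lies on Day -60 to Day 1 (SAP 9.1 and Table 2). The Year 2 course may start as late as 18 months after initiation, about Day 548 (Protocol 9.2.2). Confirmation is sought 91 to 272 days after the selected assessment (SAP 9.6). Assumed for illustration: a Year 2 start between Day 335 and Day 548, a 2-year score between Day 640 and Day 822, and no score in between.

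**Literal reading.** Let s be the Year 2 start day, b the baseline day and t the day of the 2-year score. Baseline is nearer when s − b < t − s, that is, when t > 2s − b. With b = Day 1:

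| Year 2 start s | Distance to baseline (s − 1) | Baseline picked if t is after Day 2s − 1 |
|---|---|---|
| 335 | 334 | 669 |
| 366 | 365 | 731 |
| 396 | 395 | 791 |
| 457 | 456 | 913 |
| 548 | 547 | 1095 |

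- Start on Day 366 with a 2-year score on Day 731: 731 − 366 = 365, a tie. The SAP's tie rule takes the earliest score but is written for distance from the mid-point. If carried over, it selects baseline.
- Baseline on Day -60 (there is no Day 0) is 365 + 60 = 425 days before Day 366, so the 2-year score is picked if it falls before Day 791.
- For starts on Day 457 or 548, the 2-year score is picked throughout the assumed range, up to Day 822.
- A treated patient with a baseline score and no later one always gets baseline.

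**Which pick is commoner.** A simulation took baseline as uniform on Day -60 to 1 and the next score as normal with mean Day 731 and SD 45 (all assumed). Baseline was picked in about 20% when starts were uniform on Day 350 to 400, and in about 5% when uniform on Day 350 to 548. Nearly all the rest received a score after Day 548.

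**Confirmation interval.** For an assessment on Day 366: 366 + 91 = 457 to 366 + 272 = 638. For Day 731: 822 to 1003. For a Day 1 baseline pick: 92 to 273.

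**Window applied to all.** Neither a baseline (at most Day 1) nor a score after Day 548 is eligible. All the patients above without an intermediate score are missing.

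**Effect on the summaries.** If a share p of the patients with a reported change are baseline picks, the reported mean is (1 − p) times the mean of the others. The documents give no p. For progression, SAP 9 bases proportions on the analysis set and keeps missing observations in the denominator. With k progressors among N patients in the FAS, a patient moved from missing to non-progressor leaves k/N unchanged. A 2-year pick can add to k if progression is seen and confirmed in the shifted interval.

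**The case against.** The strongest reply is that Table 2 was meant for everyone. Its row label names the treatment-start case, the introductory sentence and SAP 14.2.4 exempt nobody, baseline is a separate time-point, and Day 548 matches the latest Year 2 start described. On that reading the Year 2 start merely replaces Day 365 as the target, the Day 183 limit already forces a post-baseline score, and the harm disappears. The SAP 9 sentence on assessments from the initial date sets scope and need not override a window. All of this stands as evidence of a second reading. It does not settle the matter, because the sentence restricting the window to untreated patients says otherwise. The all-patients reading also has a defect: for a start near Day 548 the window closes at the target, so a score taken just after that start is ineligible.

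A reader might therefore infer that the SAP has adopted a rule with no time limit and no post-baseline condition. The documents support only an unresolved contradiction.

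A reader might also infer a general bias towards no worsening, or a proportionate fall in the progression percentage. Neither follows. In the simulated case most picks are later scores, which could show more worsening if disability accrues, and a baseline pick does not change the percentage under the default denominator.

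It is also fair to say that Protocol 9.1.2.2 describes EDSS as part of the routine annual assessment needed to continue treatment. Patients who went on to Year 2 may therefore usually have a score nearby. That limits the likely number affected, but the same section makes recording conditional on availability and Protocol 9.9 anticipates missing data.

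**Conclusion.** The point holds as an internal inconsistency in SAP 9.6. For a treated patient without a score near the Year 2 start, one reading gives a missing value and the other gives a baseline or roughly 2-year value. Under the literal reading the EDSS change summary is distorted, towards zero for baseline picks and in an unknown direction for later ones, and the missing count is too low. The number of patients affected cannot be computed from the documents, and the pick frequencies above rest on assumed assessment dates. Patients whose last pre-treatment score is more than 60 days before initiation have no baseline under SAP 9.1, so their change is missing on either reading. The outcome is secondary and descriptive and all measurements are listed, so this should be corrected but does not touch the primary analysis.

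**What to change.** State in SAP 9.6 that, for patients with a Year 2 course, the Year 2 EDSS is the assessment closest to the Year 2 start date among post-baseline assessments (Day 183 or later) inside a stated window. Choose one of:
- Day 183 to 548 for all patients, with the Year 2 start as the target for those treated. This is the simpler option and fits the existing table, but it excludes scores taken just after a start near Day 548.
- A window around the actual start, narrow enough not to reach the planned 2-year score. A half-width of 183 days is too wide: 548 + 183 = 731.

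Add that if no assessment qualifies the score is missing and shown in the missing category, and that for these patients the tie rule refers to the Year 2 start date and not the mid-point. The cost is a short SAP edit and one programming condition. The downside is that more patients will be shown as missing.
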